7.2 Confidentiality

All data and records generated during this study will be kept confidential in accordance with Institutional policies and HIPAA on subject privacy and that the Investigator and other site personnel will not use such data and records for any purpose other than conducting the study.

No identifiable data will be used for future study without first obtaining IRB approval. The investigator will obtain a data use agreement between provider (the PI) and any recipient researchers (including others at AHN) before sharing a limited dataset (dates and zip codes). No personal subject identifiers will be used in any presentation or publication. All data and records generated during this study will be kept confidential in accordance with Institutional policies and HIPAA on password protected institutional computers only accessed by the research team. The investigators and other site personnel will not use such data and records for any purpose other than conducting this study. All participants will be given random unique study identification numbers corresponding, but not matching, their MRN in the Epic system. The study team will have access to the subject's medical records until the records can be transferred to data sheets containing the appropriate patient study identification number.

The data will be destroyed 10 years after publication in accordance with SOP072. Any breaches in confidentiality or other problems will be identified by the study team and reported to the IRB.

7.3 Regulatory and Ethical Considerations

7.3.1 Data and Safety Monitoring Plan

The principal Investigator (P.I.) will be responsible for the ongoing data safety monitoring and oversight for the study sites. Study progress will be reviewed and submitted to the Institutional Review Board (IRB) annually.

The study would be discontinued if there is clear evidence that subjects in the early weight bearing study arm are encountering higher rates of complications compared to the control arm, non-weight bearing (NWB). This would be determined by an outside statistician ([name], LLC) that will review the data and adverse events after the first 10

patients have been enrolled in each study arm. Complications would include evidence of higher than expected non-unions, mal-union, uncontrolled pain, or wound complications, as evaluated for which specific surgical procedures were performed, any potential risk factors the patient carried, and patient compliance within the study protocol, and then treated appropriately for their risk of altered or inferior post-operative care.

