6.2 Secondary Endpoints

The secondary outcome measures are the frequency of complications during the perioperative and post-operative periods, osseous healing as assessed by both clinical and radiographic evaluation, and healing outcomes of soft tissue procedures. These results will be analyzed at the end of the follow-up period.

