Descriptive statistics on the physical and mental component scores and the eight subdomain scores from the SF-36 will be reported for the immediate weight-bearing and non-weight bearing groups. In order to examine differences in SF-36 scores within each group over time, a one-way repeated measures ANOVA will be conducted to determine if the SF-36 scores are significantly different between visits (e.g., screening, post-operative at 6-8 weeks, post-operative at 12 months, and post- operative at 24 months). A two-way repeated measures ANOVA will be conducted to determine if the SF-36 scores are significantly be conducted to determine if the SF-36 scores are significantly be conducted to determine if the SF-36 scores are significantly be conducted to determine if the SF-36 scores are significantly be conducted to determine if the SF-36 scores are significantly be conducted to determine if the SF-36 scores are significantly be conducted to determine if the SF-36 scores are significantly be conducted to determine if the SF-36 scores are significantly different between the two groups for these same visits. Post-hoc pairwise comparisons using Tukey's test or Dunn's procedure will be performed, as indicated.

Descriptive statistics on the pain, function and alignment component scores from the AOFAS will be reported for the immediate weight-bearing and non-weight bearing groups. In order to examine differences in AOFAS scores within each group over time, a one-way repeated measures ANOVA will be conducted to determine if the AOFAS scores are significantly different between visits (e.g., screening, post-operative at 6 – 8 weeks, post-operative at 12 months, and post-operative at 24 months). A two-way repeated measures ANOVA will be conducted to determine if the AOFAS scores are significantly different between visits. Post-hoc pairwise comparisons using Tukey's test or Dunn's procedure will be performed, as indicated.

The chi-square test will be used to examine the frequency of complications during the perioperative and post-operative periods, osseous healing as assessed by both clinical and radiographic evaluation and frequency of soft tissue procedures between the immediate weight-bearing and non-weight bearing groups.

Logistic regression analysis will be performed to assess which patient characteristics and surgical characteristics are associated with higher SF-36 scores and AOFAS scores.

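### The only interim comparison of complications between arms comes at 10 enrolled per arm, with no minimum follow-up and none later while the other 210 of 230 patients enrol

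*Combined protocol and SAP*

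**What the plan says.** Section 7.3.1 states the commitment without an end date: "The study would be discontinued if there is clear evidence that subjects in the early weight bearing study arm are encountering higher rates of complications" relative to the non-weight-bearing arm. The determination is given to an outside statistician, who will "review the data and adverse events after the first 10" "patients have been enrolled in each study arm". No second review, review frequency or minimum follow-up is given.

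The events in scope include healing failures: "Complications would include evidence of higher than expected non-unions, mal-union, uncontrolled pain, or wound complications". They are to be weighed "as evaluated for which specific surgical procedures were performed, any potential risk factors the patient carried, and patient compliance within the study protocol", so the review is a judgement and not a stated test.

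Other oversight continues. The principal investigator "will be responsible for the ongoing data safety monitoring and oversight for the study sites". Table 1 schedules adverse event assessment at every post-operative visit. Sections 6.6, 6.7 and 6.10 cover adverse event monitoring and reporting to the IRB, and the IRB reviews progress annually. None of this is described as a comparison of the arms.

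Section 6 contains no interim analysis. Section 6.4.1 says "The chi-square test will be used to examine the frequency of complications during the perioperative and post-operative periods", and Section 6.2 says of the secondary outcomes, complications among them, "These results will be analyzed at the end of the follow-up period". Section 3.2 sets follow-up at two years from surgery.

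**The concern.** The trigger does not match the events the review has to detect. Table 1 places randomization at the screening visit, before surgery, and Section 1.1 puts average bone and tendon healing at roughly 6 to 8 weeks. The most recently enrolled of the 20 patients may have had little or no post-operative time when the trigger is met. Pain and wound complications may already be visible. Non-union and mal-union may not be.

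After that point the commitment to stop has no described mechanism. If weight-bearing caused an excess of healing complications, it could run through the rest of enrolment without any planned arm-level look. Section 7.3.2 lists hardware failure, non-union, mal-union and delayed union as risks of the weight-bearing arm, so these are events the sponsor already has in mind.

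**Working it through.** **Plan's own figures.** Section 6.5 assumes d = 0.40, two-sided alpha .05 and 80% power. The normal approximation gives 2 x (1.960 + 0.842)^2 / 0.40^2 = 98.1, so 99 per arm. At the plan's 100 per arm, t-test power is 0.804. Adding 15 gives 115 per arm, 230 in total. The sample size reproduces and is not in question. Patients entering after the review: 230 - 2 x 10 = 210, or 210/230 = 91.3%. Because 230 is a minimum, so is 210.

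Everything below rests on assumed inputs. The protocol gives no accrual period, review date, test or expected complication rate for this review.

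**(a) How many of the 20 could be assessed for healing.** Assume even accrual of 230 over M months: r = 230/M per month, and the 20th patient enrols at t20 = 20/r = 1.04, 2.09, 3.13 or 5.22 months for M = 12, 24, 36 or 60. At a review d after the 20th enrolment, the number at least w past enrolment is min(20, max(0, (t20 + d - w) x r)), with all times in months.

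| Time past enrolment | Review date | M=12 | M=24 | M=36 | M=60 |
|---|---|---|---|---|---|
| 6 weeks | same day | 0 | 6.8 | 11.2 | 14.7 |
| 6 weeks | 4 weeks later | 11.2 | 15.6 | 17.1 | 18.2 |
| 6 weeks | 8 weeks later | 20 | 20 | 20 | 20 |
| 3 months | same day | 0 | 0 | 0.8 | 8.5 |
| 3 months | 4 weeks later | 0 | 0.1 | 6.7 | 12.0 |
| 3 months | 8 weeks later | 0 | 8.9 | 12.6 | 15.6 |

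These count from enrolment. A 4-week wait for surgery moves each row back to the one above it within its block. A slow start to recruitment raises the counts.

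**(b) Information in 10 per arm, no test assumed.** Newcombe 95% limits for the rate difference, with complete follow-up:
- 3/10 against 1/10: 20.0 points (-16.0 to +51.4).
- 17/57 against 6/57, about the same rates at half of planned enrolment: 19.3 points (+4.5 to +33.3).
- With no events in 10 patients, the one-sided 95% upper bound on that arm's rate is 1 - 0.05^(1/10) = 25.9%.

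**(c) If Fisher's exact test at .05 were used.** At 10 per arm a two-sided result needs, for example, 5 against 0 (p = 0.033); 4 against 0 gives p = 0.087. The probability of flagging an excess in the weight-bearing arm, by exact enumeration with a 10% control rate, is as follows (one-sided in brackets):

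| True rates | 10 per arm | 57 per arm |
|---|---|---|
| 30% v 10% | 5.7% (14.3%) | 70% (81%) |
| 20% v 10% | 1.2% (4.5%) | 23% (35%) |

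**(d) Whether added looks could still change anything.**
- When the 20th patient is 3 months past enrolment, 20 + 3r = 78, 49, 39 or 32 patients are enrolled. Delaying the existing look to that point would lose early warning, so it should be added to and not replaced.
- A look on 57 per arm (114 patients) with 3 months' follow-up falls at 114 + 3r = 172, 143, 133 or 126 enrolled, leaving about 58 to 104 still to enter. With a 4-week wait for surgery, 41 to 101 are left.

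**The case against.** Five points can be made against this.

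- **Reading.** The text fixes when review starts and does not say it happens once. A look at non-unions on enrolment day makes little sense, so a later or continuing review may be intended. That is possible, but no later date or frequency appears anywhere. If it is the intent, writing it down is the remedy.
- **Other oversight.** No blinding is described, the arms are visibly different, and the data form records study group, so the investigator can see events by arm. Sections 6.9.1, 6.10 and 6.10.1 add causality grading, prompt IRB notice and follow-up of serious events, and Sections 4.4 and 4.5 allow withdrawal for safety. This stands as protection for individual patients. It does not supply the rate comparison on which the commitment to stop depends.
- **Proportionality.** The number of safety looks is a design choice, and the sponsor regards the added risk as minimal (Sections 7.3.2 and 7.3.4). This is fair, and the number and timing are left to the sponsor. But the protocol itself chose a rule based on comparing the arms.
- **Assumptions.** The follow-up gap could be large or nil: if the review falls 8 weeks after the 20th enrolment and surgery is immediate, all 20 are past 6 weeks. One pooled rate is also crude for mixed bone and soft-tissue surgery, and a reviewer exercising judgement could act on a cluster short of significance. All of this stands. The figures show a range and do not predict an outcome.
- **Limits of the remedy.** One added look at 57 per arm would usually miss a doubling from 10% to 20%. It is still far more informative than 10 per arm.

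**Conclusion.** The concern holds. As written, the only interim arm comparison can be completed before healing complications are assessable, and nothing comparable is described until the end of follow-up, with at least 210 of 230 patients (91%) entering in between. That much follows from the text alone.

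The size of the healing-data gap depends on assumed accrual and review timing: from 0 to about 15 of 20 patients six weeks past enrolment at a same-day review, and up to all 20 at a review 8 weeks later. The low information in 10 per arm does not depend on accrual, since limits of -16 to +51 points around an observed 20-point excess assume complete follow-up. The sponsor should change this. The consequence is delayed recognition of an arm-level excess; individual serious events would still reach the investigator and the IRB.

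**What to change.** In Section 7.3.1:

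1. Keep the review at 10 per arm, and say it is for early events such as pain and wound complications.
2. Add harm-only comparisons by the same outside statistician. The first should come when those 20 patients have completed a post-operative visit at which healing can be assessed (for example the 3-month visit), and at least one more before enrolment closes. Number and timing are for the sponsor.
3. At each look, report complication counts by arm, the rate difference and a confidence limit for all randomised patients, alongside the existing review by procedure, risk factors and compliance. What counts as sufficient evidence to stop remains the sponsor's decision.

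**Cost.** Statistician time, chart abstraction across five sites at each added look, and new wording. The data form already carries study group and visit. Harm-only looks spend no efficacy alpha.

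There is some risk of a false alarm. If Fisher's test at .05 were applied unadjusted with equal true rates, 400,000 simulated trials give the following chance of a false signal against weight-bearing (one-sided in brackets):

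| Looks, per arm | 5% rates | 10% rates | 20% rates |
|---|---|---|---|
| 10, 57 | 0.5% (1.4%) | 1.1% (3.0%) | 1.7% (4.3%) |
| 10, 29, 57, 86 | 1.2% (3.2%) | 2.3% (5.2%) | 3.3% (7.1%) |

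The highest figure, 7.1%, is a reason to choose the number of looks and the standard of evidence together.

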1 BACKGROUND INFORMATION AND RATIONALE

1.1 Introduction

There is an ongoing debate within the surgical community as to whether it is best to keep patients who have undergone foot and ankle surgery non-weight-bearing (NWB) for an extended period of time versus allowing them to bear weight early, or on occasion, immediately. The standard for many foot and ankle procedures involving fusion of bone and repair of ligaments and tendons has been to keep the patient completely NWB for 6-8 weeks, or the approximate time it takes for bone and tendon to heal, on average. This standard has been challenged in recent years, with more surgeons allowing their patients to bear weight earlier than previously considered safe. Our aim is to assess if immediate weightbearing following any foot and ankle procedure is equally as safe and effective as an extended course of NWB in patients meeting our inclusion criteria.

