
a plaster cast for 2 weeks, followed by a boot with traditional wedge progression until they reached a plantigrade orientation after 4 additional weeks. In their microdialysis analysis, they found that the healing tendons in both groups exhibited increased levels of metabolites glutamate, lactate, and pyruvate, compared to the subject's contralateral tendon, but the functional weight-bearing group had a significantly higher concentration of glutamate compared to the non-weight-bearing cast group. This correlated to improved functional outcomes at 6 months, and supported their conclusion that functional weight-bearing enhances early healing response after Achilles tendon repair. (10)

In the review of the literature, two separate systemic reviews were identified, which support early weight-bearing after ankle fracture repair when compared to late weightbearing or non-weight-bearing for six weeks following surgery. These reviews found no significant adverse results in the early weight-bearing groups, while finding earlier return to previous activities and earlier return to work. (11,12). Additionally, Assal et al. was able to show that, with augmented fixation, early weight-bearing in older patients (greater than 70) with Weber B ankle fractures was a safe and satisfactory method of postoperative care. (13) Starkweather et al. found no malunions or nonunions, and a 9.5% complication rate in patients allowed to be protective weight-bearing following ankle fracture ORIF, while Firoozabadi et al. saw a complication rate of 8% and a loss of correction in only 1 of 26 (4%) patients allowed to immediately bear weight following ankle ORIF. (14, 15) In a randomized control trial, Dehghan et al. divided 110 patients into an early WB group (2 weeks) and a late WB group (6 weeks) and assessed time to return to work, SF-36 scores, and rates of complications. They found no difference in return to work between the two groups, but the early WB group showed significantly improved SF-36 scores on both physical and mental components. Early WB was also found to have similar wound complication rates, with no cases of fixation failure or loss of reduction. The late WB group additionally showed higher rates of hardware removal due to irritation. (19% vs 2%) (16)

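### The only study-stopping criterion (Section 7.3.1) rests on one review at 10 patients enrolled per arm, with no threshold, an undefined expected rate and no later interim comparison, so it cannot separate harm from chance

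*Combined protocol and SAP*

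**What the plan says.** Section 7.3.1 contains one discontinuation sentence. The standard of proof is clear evidence, and the comparison is stated as: "subjects in the early weight bearing study arm are encountering higher rates of complications compared to the control arm". The determination is given to an outside statistician, whose one scheduled task is to "review the data and adverse events after the first 10", with the 10 counted per arm and by enrolment. The section then describes what counts: "Complications would include evidence of higher than expected non-unions, mal-union, uncontrolled pain, or wound complications". That description carries a case-mix qualifier: "as evaluated for which specific surgical procedures were performed, any potential risk factors the patient carried, and patient compliance within the study protocol".

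The section gives no test, significance level, event count, boundary or expected rate. It makes the principal investigator responsible for ongoing safety oversight and sends study progress to the IRB once a year, but it does not ask for another comparison of the arms. Section 6.2 places the formal analysis of complications at the end of follow-up.

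Safety is a central question of the trial. Section 1.1 aims to assess whether immediate weight-bearing "is equally as safe and effective as an extended course of NWB in patients meeting our inclusion criteria". Section 7.3.4 accepts that complication risk may be slightly raised in the study group.

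**The concern.** A stopping criterion is useful only if the review that applies it can tell a harmful arm from an unlucky one. Here the whole determination falls on 20 patients, without a stated standard of evidence. If the standard is strict, even a large true excess will almost always go unnoticed. If it is loose, chance alone will often raise an alarm. The unquantified reference to what is expected widens that range, and two competent statisticians could decide differently on the same 20 patients.

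At stake is the safety of the remaining patients, up to the planned 115 per arm. There is also a risk that an uneventful early review is later cited as support for equal safety, which it could not provide.

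**Working it through.** **The plan's own figure.** The only power statement is in Section 6.5: 100 per group for 80% power at d = 0.40, two-sided 0.05. It reproduces: the exact t-test calculation gives 99.08 per group, and power at 100 is 80.4%. It concerns the questionnaires. No operating characteristic is given for the safety review, so there is none to reproduce.

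**Inputs**
- Size at review: 10 per arm (7.3.1).
- Test and level: Fisher's exact test and two-tailed p<.05 are the general conventions in 6.4.1. Applying them to the safety review is an assumption, because 6.4.1 does not tie them to it.
- Control rate: 8% and 9.5%, assumed from two ankle-fracture fixation series in Section 1.2, one of them reporting "a 9.5% complication rate in patients allowed to be protective weight-bearing following ankle fracture ORIF". The trial's mix of procedures is wider.
- Independent patients, all with complete follow-up. This favours the plan, since the review is triggered by enrolment and non-union may not yet be visible.

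**Step 1: what a control-arm test needs.** For 4 v 0, one-sided p = C(10,4)/C(20,4) = 210/4845 = 0.043, so two-sided p = 0.087. For 5 v 0, one-sided p = C(10,5)/C(20,5) = 252/15504 = 0.016, so two-sided p = 0.033. The smallest tables significant two-sided are 5 v 0, 7 v 1, 8 v 2 and 9 v 3. One-sided, they start at 4 v 0 and 6 v 1.

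**Step 2: how often it signals.** Sum Bin(a; 10, p_WB) × Bin(b; 10, p_NWB) over the significant tables with a > b.

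| Control rate | Test | No effect | Doubled | Tripled |
|---|---|---|---|---|
| 8% | two-sided | 0.03% | 0.6% | 3.0% |
| 9.5% | two-sided | 0.05% | 1.0% | 5.0% |
| 8% | one-sided | 0.25% | 2.7% | 9.4% |
| 9.5% | one-sided | 0.40% | 4.0% | 13.0% |

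A tripling is therefore missed 95-97% of the time two-sided and 87-91% one-sided. For scale, 80% power for a doubling needs about 258 per arm from 8% and 212 per arm from 9.5%.

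**Step 3: the expected-rate wording.** Let X be the number of weight-bearing patients of 10 with a complication, and p the assumed expected rate. With no treatment effect:
- Any excess over 10p, P(X > 10p): 40% at p = 5%, 57% at 8%, 63% at 9.5%, 26% at 10%, 46% at 15%, 32% at 20%. For example, 1 - 0.905^10 = 0.631. The fall between 9.5% and 10% arises because two events, not one, are then needed to exceed 10p.
- At least two events: 19% at 8%, 24% at 9.5%.
- One-sided 5% exact binomial test: 3 of 10 needed at 8% (4.0%), 4 of 10 at 9.5% (1.1%).

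So the false-alarm rate runs from about 1% to about 63%, according to the reading and the assumed rate.

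**Step 4: what a clean review shows.** With 0 of 10 complications, the one-sided 95% upper limit is 1 - 0.05^(1/10) = 25.9%.

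**Step 5: does cumulative monitoring help?** Illustration only: signal when the posterior probability that the weight-bearing rate exceeds the control rate is above 0.975, with Beta(0.5, 0.5) priors and a 9.5% control rate. The looks, at 10, 30, 60 and 90 per arm, are assumed because no accrual rate is given. Cumulative signal probability from 20,000 simulations:

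| True effect | 10 | 30 | 60 | 90 |
|---|---|---|---|---|
| None | 2.4% | 4.6% | 6.6% | 7.7% |
| Doubled | 11.9% | 24.5% | 42.2% | 54.9% |
| Tripled | 26.7% | 54.4% | 83.2% | 94.3% |

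A repeat with 40,000 simulations gave final values of about 7%, 54-55% and 94%. At the first look this boundary signals at 3 v 0 (posterior 0.976), where Fisher's two-sided p is 0.21.

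**The case against.** Several points on the other side stand.

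- A reader might infer that 7.3.1 sets two conflicting stopping rules. The text does not support that. The discontinuation sentence names only the control arm. The expected-rate phrase belongs to the description of complications and carries a qualifier for procedure, risk factors and compliance, so it may be no more than a case-mix adjustment. What remains is an unexplained relation between two sentences.
- A reader might also infer that the expected-rate reading would stop a harmless trial more often than not. That needs an assumed rate the plan does not give, and any single event to count as an excess. It fails at 5%, 10%, 15% and 20%, and falls to 1-4% under a one-sided 5% test. Setting a significance test on one reference against a bare excess on the other is an unequal comparison, since clear evidence governs the decision.
- The p<.05 convention is imported, and the 8-9.5% rates come from a narrower group of operations.
- The review is not the only safeguard. There are also investigator oversight, annual IRB review, adverse event reporting (6.7, 6.10) and withdrawal for safety (4.5).

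None of this gives the review a threshold, or makes 10 per arm informative. Holding both references to one strict standard removes the contrast between them, but the control-arm check still misses most triplings. The other safeguards do not schedule a comparison of the arms.

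**Conclusion.** The concern holds as a matter of an undefined criterion applied once, at a size that cannot support it. Under a conventional test against the control arm, the review would signal in about 1% or less of trials in which the complication rate doubled and 3-5% in which it tripled (3-4% and 9-13% one-sided). The expected-rate wording adds ambiguity, with false-alarm rates between about 1% and 63%. These figures rest on assumed control rates of 8-9.5%, one overall complication rate per arm, complete follow-up, and a significance convention that the plan does not assign to safety. The documents do not support a claim of contradictory rules, or of a rule that usually fires without cause.

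**What to change.** In Section 7.3.1:

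1. Reconcile the discontinuation sentence with the sentence describing complications, so that it is clear how the expected-rate wording relates to the control-arm comparison.
2. Keep the 10-per-arm review. Have the outside statistician repeat the between-arm comparison at each annual IRB review already scheduled, on cumulative per-arm counts of patients with any listed complication.
3. Use one pre-stated numerical boundary at every look, chosen by the sponsor and the IRB, and report its operating characteristics for the looks actually planned. The posterior-probability example shows only that a workable boundary exists; its figures must be recomputed for the real schedule. No second threshold should be written in for the first look.
4. State that passing the 10-per-arm look is not evidence of equal safety.

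The cost is protocol wording, one boundary calculation and a short yearly analysis by the statistician already engaged. No extra patients, visits or procedures are needed. The downside is a small, stated chance of a false stop signal, about 7-8% over all looks in the illustration. Detection of a doubling stays moderate there, at 54-55%.
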